culprit lesions.²² The combination of stenosis + atheroma burden + luminal area produced an odds ratio of 3.99 (95% CI: 1.74-9.13, p=0.001) for culprit plaque. The GLAGOV study showed that PCKS9 inhibition reduced the percent atheroma volume of coronary arteries over a 78 week treatment period.²³ With atheroma volume now established as a viable biomarker, vwMRI is the optimal test to monitor it and stenosis, both for ICAD and in other locations of the cerebrovasculature, such as the carotid arteries, cervical vertebral arteries, and aortic arch.

A.5. Impact

The result of this study will be a dataset that lays the foundation for a randomized controlled trial of Repatha in ICAD patients. The data collected in this study will allow us to optimize a future clinical trial designed to demonstrate a reduction in stroke risk, ultimately making more efficient and economical progress towards our ultimate research goal of preventing stroke with Repatha. While we are proposing future studies to reduce ICAD stroke risk, it should be noted that our study will also evaluate the potential for Repatha to decrease cerebrovasculature stenosis and plaque burden, which would be a compelling primary prevention indication.

B. Approach

B.1. Study Hypothesis

We hypothesize that inhibition of PCSK9 with Repatha in patients with moderate to severe intracranial atherosclerosis will reduce validated biomarkers of stroke risk (stenosis and percent atheroma volume). To answer our hypothesis, we propose a single arm study of Repatha in 150 patients with a prior history of ischemic stroke and ICAD causing at least 50% stenosis of a major intracranial artery in the Circle of Willis ("index artery").

B.2. Study Design

We will enroll 150 ICAD patients with a prior history of ischemic stroke. Patients will be enrolled at up to 8 medical centers in North America. All patients will receive Repatha for 78 weeks and will have an MRI before beginning study medication and a comparison MRI immediately after completing study medication.

B.3. Investigational Treatment

The investigational treatment is Repatha 140 mg administered subcutaneously with a single-dose pre-filled pen syringe every 2 weeks for a total of 39 treatments. Dose modification is not allowed.

B.3.a. Inclusion Criteria

- Adult patients, ≥ 18 years of age

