- History of ischemic stroke, defined as an episode of neurological dysfunction caused by focal cerebral, spinal, or retinal infarction (American Heart Association definition).
- Large vessel atherosclerosis of an intracranial artery in the circle of Willis with 50-99% stenosis by WASID criteria (percent stenosis = (1-[diameter stenosis/diameter normal]) x 100%) on MRA, CTA or DSA
 - Eligible arteries: vertebral (V4), basilar, PCA (P1, P2), MCA (M1, M2), tICA, ACA (A1)
- Current statin use or contraindication to statin
- Fasting LDL-C ≥ 70 mg/dL or LDL-C ≥ 60 mg/dL if lipoprotein (a) > 30 mg/dL; within a year of randomization and on the current statin medication/dose

B.3.b. Exclusion Criteria

- Gadolinium or PCSK9 inhibitor allergy
- Acute or chronic kidney disease with eGFR<30 ml/min/1.73m²
- Pacemaker or other MRI contraindications per American College of Radiology guidelines²⁴
- Inability to return for 78 week follow-up clinic visit and vwMRI

Pregnant at time of enrollment

B.4. Investigational New Drug Status

We will not require an IND. Repatha is indicated to reduce the risk of myocardial infarction, stroke, and coronary revascularization in adults with established cardiovascular disease; and as an adjunct to diet, alone or in combination with other lipid-lowering therapies (e.g., statins, ezetimibe), for treatment of adults with primary hyperlipidemia to reduce low-density lipoprotein cholesterol (LDL-C). Our patient population meets these criteria given 1) history of ischemic stroke and 2) presence of moderate to severe ICAD.

B.5. Patient Recruitment

Patients will be approached first by a member of their clinical care team in order to gain permission for a study member to approach to discuss the study in detail. Only co-investigators or study coordinators on this study will consent patients. Standard consenting procedures will be followed, including giving patients and family members adequate time to discuss the study with the study team and amongst themselves prior to consenting. A full, written, IRB- approved Informed Consent document will be provided to the patient (or representative) for signature after the patient or patient's representative has had time to read it and ask questions. A copy will be given to the patient for his/her records. Proxy consent by legally authorized representatives will be allowed in the case of post-stroke aphasia or other cognitive disability, in order to not bias study entry by stroke severity.

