
C.2.a. Secondary endpoint 1 measurement:

a) ICAD post-contrast plaque enhancement (PPE): is a dichotomous variable evaluated on the T1 pre- and post-gadolinium sequences, with multiplanar reconstruction so the ICAD can be seen in cross section.²⁶ PPE is defined by placing a region-of-interest over areas of gadolinium enhancement in ICAD to evaluate if it is equal to or exceeds the signal intensity of the pituitary infundibulum, as previously described.²⁷

- b) Carotid intraplaque hemorrhage (IPH): MPRAGE positive plaque is defined as voxels with at least 2-fold signal intensity compared to sternocleidomastoid muscle as previously described. MPRAGE positive plaques can be reliably identified. Kappa values for inter- and intra-rater reliability for detection of MPRAGE positive plaque were 0.806 and 0.818 respectively (very good agreement).^{28,29}
- c) MRA Flow Dynamics (**MFD**): We will measure MFD using accepted quantitative MRA methodology. The VERiTAS study provided prospective confirmation of the importance of MFD as a biomarker of stroke risk for patients with ICAD. Given that MFD can easily be measured in our vwMRI protocol, we will acquire the data required for its quantification.

C.3. Secondary endpoint 2

To better understand the mechanism of Repatha's effect on intra- and extracranial atherosclerosis, we will measure the endpoint of change in cholesterol markers [LDL-C, HDL-C, lipoprotein (a), apolipoprotein B, and triglyceride level]. The change in cholesterol markers will be correlated with the primary and secondary study endpoints on vwMRI. Cholesterol values will be measured at the baseline and comparison MRIs, which are 78 weeks apart. If standard of care lab values are available within 30 days of the study visit, they can be used in place of the study lab value. An additional exploratory outcome that we will measure is the composite endpoint of "recurrent stroke," which encompasses new patient-reported symptomatic ischemic stroke, transient ischemic attack, or asymptomatic strokes that emerge between MRIs.

C.3.a. Secondary endpoint 2 measurement:

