- a) At both study MRIs, the study coordinator may collect two blood samples. Standard of care lab values can be used in place of these tests, if the values are from within 30 days of the study visit. If standard of care labs are not available, then the following samples will be tested. One sample may be tested with an i-STAT for creatinine levels prior to the MRI and, in women of child-bearing age who are not on birth control, a bHCG should be tested. The second sample may be sent for testing of LDL-C, HDL-C, triglycerides, apolipoprotein B, and lipoprotein (a), biomarkers of cardiovascular disease risk.
- b) At both study visits (baseline vwMRI and follow-up vwMRI), a physician will assess patients and their medical records for stroke. The physician will also have access to the data from the neuroradiologist raters. The endpoint of stroke is defined for all arterial distributions in the cerebrovasculature.

C.4. Data Collection and Management

Baseline and follow-up patient data are written on a case report form and then entered into a REDCap case report form (**eCRF**) based on the NIH Stroke Common Data Elements (CDE). We will also complete CRFs based on the "Demographics," "Health History," "Prior Health Status," and "Drugs" forms,²⁵ and utilize the SNOMED coding system for comorbidities.³⁰ All data analysis is conducted with Stata.

D. Methodology

D.1. Statistical methods

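### Routine lipid results may replace either study sample subject only to a 30-day window, so a patient's change in lipoprotein(a) can include a between-assay difference

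*Combined protocol and SAP*

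**What the plan says.** Section C.3 defines the endpoint: "we will measure the endpoint of change in cholesterol markers [LDL-C, HDL-C, lipoprotein (a), apolipoprotein B, and triglyceride level". On timing it says: "Cholesterol values will be measured at the baseline and comparison MRIs, which are 78 weeks apart". Each patient's change is therefore one difference between two single results.

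C.3 then allows substitution: "If standard of care lab values are available within 30 days of the study visit, they can be used in place of the study lab" result. C.3.a, item a, repeats the rule for both study MRIs: "Standard of care lab values can be used in place of these tests, if the values are from within 30 days of the study visit". It also sets the order of preference: "If standard of care labs are not available, then the following samples will be tested". The routine result is thus the first choice and the study sample the fallback, separately at each visit.

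For the study sample itself, C.3.a says: "The second sample may be sent for testing of LDL-C, HDL-C, triglycerides, apolipoprotein B, and lipoprotein (a), biomarkers of cardiovascular disease risk". No laboratory or assay is named. B.2 says: "Patients will be enrolled at up to 8 medical centers in North America". The only lipid units in the plan are in the eligibility criterion in B.3.a: "Fasting LDL-C ≥ 70 mg/dL or LDL-C ≥ 60 mg/dL if lipoprotein (a) > 30 mg/dL".

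The values have two uses. C.3 correlates the changes with the vessel wall MRI endpoints. D.1 uses on-treatment LDL-C, HDL-C and lipoprotein(a) as predictors, and D.2 plans to replicate a relationship with on-treatment LDL-C.

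**The concern.** A change score is interpretable only if both values are on the same scale. Under this rule, the baseline value may come from one laboratory and the week-78 value from another. Any systematic difference between the two methods then counts as change in the patient.

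Random assay differences weaken the correlation between lipid change and plaque change, which is the stated mechanism analysis. Differences in one direction shift the mean change, and a single-arm study has no concurrent control group in which the shift would cancel. Analysts cannot repair a mixed pair afterwards, and the plan does not ask for the information needed to identify one.

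The imaging side shows the contrast: C.1.a specifies field strength, coil, sequences and measurement software. The lipid side has no equivalent.

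**Working it through.** **1. Text check.** I looked through the whole document for any rule on laboratory, assay, units, conversion or recording of source laboratory for the lipid markers. There is none. E.12 mentions certification and quality control of supporting laboratories, but only as records open to audit. The 30-day window is the sole condition on substitution.

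**2. No figure to reproduce.** The plan gives no sample size, SD or expected effect for the lipid endpoint, and no between-assay difference. Everything below is an illustration for lipoprotein(a) on assumed inputs:
- true change -25%;
- two assays differing by a proportion b of 10-20%;
- a share p of 25-50% of patients with a mixed pair;
- true SD of percent change 15 points;
- assay differences falling in either direction at random.

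C.3 does not say whether change is absolute or percent; I use percent.

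**3. Error in one mixed pair.** The assay difference acts on a week-78 value that is 75% of baseline, so the error in points is s = 0.75 × b.
- b = 10%: s = 7.5 points. The pair reads 0.75 × 0.90 - 1 = -32.5% to 0.75 × 1.10 - 1 = -17.5%.
- b = 20%: s = 15 points. The pair reads 0.75 × 0.80 - 1 = -40% to 0.75 × 1.20 - 1 = -10%.

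**4. Reliability and correlation.** Reliability = 15² / (15² + p × s²). With error in one of the two variables, the correlation is multiplied by the square root of the reliability.

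| p | s (points) | Reliability | Correlation multiplied by |
|---|---|---|---|
| 0.25 | 7.5 | 225 / (225 + 14.1) = 0.94 | 0.97 |
| 0.50 | 7.5 | 225 / (225 + 28.1) = 0.89 | 0.94 |
| 0.25 | 15 | 225 / (225 + 56.3) = 0.80 | 0.89 |
| 0.50 | 15 | 225 / (225 + 112.5) = 0.67 | 0.82 |

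**5. How far the assumptions carry this.**
- b = 5% and p = 0.25: s = 3.75, reliability 225 / (225 + 3.5) = 0.98, correlation factor 0.99.
- b = 30% and p = 0.50: s = 22.5, reliability 225 / (225 + 253.1) = 0.47, correlation factor 0.69.
- True SD 25 points with the inputs of step 4: reliability 625 / (625 + 14.1) = 0.98 to 625 / (625 + 112.5) = 0.85, correlation factor 0.99 to 0.92.
- No mixed pairs: no loss.

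**6. Differences in one direction.** If all switches go the same way, the mean change moves by p × s: from 0.25 × 7.5 = 1.9 points to 0.50 × 15 = 7.5 points, against an assumed true change of -25%.

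**7. LDL-C.** The error in points is b times the fraction of the marker that remains at week 78. The background section expects a dramatic fall in LDL-C, so the same proportional assay difference gives a smaller error against a larger change.

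**The case against.** The best defence is that this is a pragmatic rule for a secondary, mechanistic endpoint, with a harm of unknown size. B.5 has the patient's own clinical team make the first approach, so many routine results may come from the enrolling center's laboratory at both visits. The share of mixed pairs is assumed. LDL-C should be little affected, and the comparison of stenosis and PAV with 0% change uses no lipid value at all. On this view it would be enough to record the source laboratory and add a sensitivity analysis.

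Most of this stands as a limit on size and importance. It does not remove the gap. That both results come from the enrolling center is an inference; the plan does not require it. A sensitivity analysis alone would identify mixed pairs only to leave them out, whereas the blood draw that B.9 schedules at both visits could prevent them.

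A simpler remedy is also open to objection, rightly. Requiring routine values to match within a patient, and otherwise running the study sample, fails because a mismatch is known only at week 78. By then a baseline study sample that was never tested or stored cannot be recovered. Within-patient matching also does not protect the D.1 models, which compare on-treatment values across patients.

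**Conclusion.** The concern holds for secondary endpoint 2. The stated rule allows a between-assay difference into the change score, chiefly for lipoprotein(a). On the assumptions in the working, the correlation with imaging change is multiplied by about 0.97-0.82; wider assumptions give anything from almost no loss to about 0.69. The direction of the effect is clear, but the documents cannot fix its size.

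Four stronger readings are tempting and not supported:
- **Reliability of 0.90-0.53, with a slope reduced by the same factor.** This needs errors of 10-20 points, but a 10-20% assay difference on a value at 75% of baseline is 7.5-15 points. C.3 also specifies a correlation with change, not a regression on it.
- **A true -25% reading anywhere from -40% to -6% through mixed mass and molar lipoprotein(a) units.** The documents mention only mg/dL and no conversion, so this rests on outside facts and an assumed conversion factor of 2.0-2.5.
- **The same attenuation in D.1's on-treatment models.** The relevant quantity there is the between-patient spread of on-treatment values, which the documents do not give. The models are exposed, but no figure can be put on it.
- **Damage to the main result.** The comparison of stenosis and PAV with 0% change does not depend on lipid values.

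**What to change.** Amend C.3 and C.3.a as follows.

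- For the endpoint, draw and test the study sample at both visits in one laboratory and assay per patient, with one lipoprotein(a) unit and assay type across the study. Alternatively, store a baseline aliquot so that both samples can be run together at week 78.
- Limit routine values to safety or eligibility use, or to cases where laboratory, assay and units match the patient's other value.
- Record source laboratory, assay and units on the eCRF for every lipid value, and do not convert lipoprotein(a) between units.
- In D.1, repeat the change and on-treatment analyses using only same-laboratory, same-assay values.

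The cost is more than wording: some extra assays or aliquot storage for patients who already have routine results, and a few values left out of the sensitivity analysis. C.3.a already provides for the tube, and B.9 already schedules blood draws at both visits.

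### As written, the 30-day lab substitution in C.3.a also covers the baseline bHCG, and a result that old cannot establish the pregnancy exclusion before gadolinium and first dose

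*Combined protocol and SAP*

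**What the plan says.** C.3.a, item a, sets out the blood work in this order.

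- It opens with both samples: "At both study MRIs, the study coordinator may collect two blood samples".
- The substitution rule comes next: "Standard of care lab values can be used in place of these tests, if the values are from within 30 days" of the visit.
- Fresh testing is then made conditional: "If standard of care labs are not available, then the following samples will be tested".
- Only after that are the samples described. The first is for creatinine ("One sample may be tested with an i-STAT for creatinine levels prior to the MRI") and pregnancy ("in women of child-bearing age who are not on birth control, a bHCG should be tested"). The second is for LDL-C, HDL-C, triglycerides, apolipoprotein B and lipoprotein (a).

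B.3.b lists the exclusions that these tests serve: "Pregnant at time of enrollment" and "Acute or chronic kidney disease with eGFR<30" (ml/min/1.73m²). Under C.1.a every vessel wall MRI uses gadolinium, and under B.8 study drug is handed over at the baseline visit. Figure 1 marks a pregnancy test at Screen/Baseline, with no statement of how recent it must be.

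**The concern.** For lipids, a routine value up to a month old is a reasonable convenience. A pregnancy test has a different job: it must show the woman's status on the day when she is enrolled, given contrast and started on drug. The rule does not separate the two uses. A site that follows the text could accept a negative bHCG taken before a conception and then go ahead with gadolinium and the first injection. What is at stake is avoidable exposure of an early pregnancy at baseline. The estimates of the trial are not at stake.

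**Working it through.** No arithmetic bears on whether the point holds, and the plan states no figure to reproduce. The check is whether the text allows the older bHCG and whether any other section closes the gap.

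**1. Which tests does the rule cover?** In C.3.a the rule follows the announcement of two samples and precedes the description of both. The next sentence tests the samples only when routine results are lacking. The bHCG belongs to the first of those samples, and no test is carved out. Read literally, the rule covers creatinine, bHCG and lipids.

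**2. What was probably meant?** C.3 contains the same 30-day allowance directly after a sentence on when cholesterol values are measured. That points to a lipid-only intention. C.3.a, however, is the text that tells the coordinator what to do with the blood samples, and there the limit to lipids is lost.

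**3. Does another section require a current bHCG?**

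| Section | What it provides | Does it require a current bHCG before contrast and first dose? |
|---|---|---|
| B.3.b | Excludes women pregnant at enrolment | No. It sets the condition, not the test or its age |
| Figure 1 | Pregnancy test marked at Screen/Baseline | No. No window is given, and C.3.a is the only text on how the test is met |
| B.9 | Physician evaluation and blood draw with each scan | No. It gives an opportunity to test, not an instruction |
| C.1.a | Gadolinium at every scan | No |
| B.8 | Drug given at the baseline visit | No |
| E.5 | Drug stopped once pregnancy is confirmed | No. It acts after exposure |

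**4. What does the allowed age mean?** Put the baseline visit at day 0. The rule accepts a negative result from as early as day −30. A pregnancy that begins, or becomes detectable, between that test and day 0 is invisible to it. A test at the visit removes this added period of up to 30 days. It is not perfect either, since a very recent conception may not yet show, but it is the closest available match to an exclusion defined at enrolment.

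**5. How many women would need a baseline bHCG?** The documents do not give the number of women of child-bearing age who are not on birth control. Assume 2% to 10% of the 150 patients:

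- 150 × 0.02 = 3 women
- 150 × 0.10 = 15 women

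So there would be about 3 to 15 baseline tests, all of a kind already marked in Figure 1. Only those women who also have a routine bHCG from the past 30 days would need an extra test. This range serves the costing alone and is not evidence of harm.

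**The case against.** The strongest reply is that the rule was never meant for safety tests. It sits under a secondary lipid endpoint, and its counterpart in C.3 concerns cholesterol. The verbs in C.3.a also differ: creatinine and lipids may be tested, while the bHCG should be. The point about intention stands, and most sites might act on it. But the stronger verb still comes under the condition that routine results are lacking, and a clause that needs its intention inferred is worth rewording.

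Second, safeguards exist. B.3.b still binds, a physician sees each patient at the visit, and MRI contraindications under the cited radiology guidelines exclude a patient. E.5 stops the drug on confirmation, requires a report within 10 calendar days and makes follow-up of the pregnancy mandatory. All of this stands, and E.5 limits continued drug exposure. It does not reach the unsuspected pregnancy at baseline, where contrast and the first dose have already been given.

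Third, the reach is narrow. If no routine bHCG exists, C.3.a itself calls for testing. This stands too, and it is why the severity is low.

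A reader might also infer stronger points that the documents do not support:

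- **That 30 days is too old for creatinine.** The same sentence covers creatinine, and an older value cannot rule out acute disease. But it does inform chronic disease, suspected acute disease can be tested, and no section supplies a standard against which 30 days fails. A shorter window would be a preference.
- **That a value obtained after the visit could be used.** The phrase "if the values are from within 30 days of the study visit" gives no direction. Yet creatinine is placed before the MRI, and a later result cannot serve an exclusion judged at enrolment. This adds little for the safety tests.
- **That the screening test may long precede the scan.** Figure 1 puts the test under Screen/Baseline and the scan under Day 1, but B.9 describes a single in-person baseline visit with scan, evaluation and blood draw together.
- **That week 78 shows the same defect.** Figure 1 has no pregnancy test at Day 546, although C.3.a speaks of both MRIs. That is a separate mismatch in the documents and does not support the baseline point.

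**Conclusion.** The point holds in a limited form. As written, C.3.a lets a routine bHCG up to 30 days old stand in for the baseline test, and no other section requires a current one before gadolinium and first dose. Such a result does not establish that a woman is not pregnant at enrolment.

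It would go too far to say that the plan permits the enrolment of pregnant women. The exclusion remains in force; the weakness lies in the evidence accepted for it.

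Harm needs three things together: a recent routine bHCG, an intervening conception and no clinical suspicion at the visit. The documents give no frequency for any of them, so the size can be described only as small. The conclusion rests on the literal reading of C.3.a, with a lipid-only intention acknowledged as likely. There is no effect on the primary endpoints, power or loss to follow-up. Low severity.

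**What to change.** In C.3.a, item a:

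1. State that the 30-day substitution applies only to LDL-C, HDL-C, triglycerides, apolipoprotein B and lipoprotein (a).
2. Require the bHCG, in the women to whom C.3.a already applies it, at the baseline visit, with the result known before contrast and before the first dose.
3. Optionally, use the planned i-STAT creatinine before contrast when acute kidney disease is possible.

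The cost is a few words in one paragraph. B.9 already plans a blood draw with the baseline scan, and Figure 1 already marks the pregnancy test there. The downside is a repeat test in the few women who have a recent routine bHCG. Sites keep the 30-day convenience for lipids.

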We will fit a mixed effects linear regression model, specifically a LOESS smoothing curve, to change in stenosis/PAV and on-treatment LDL-C, HDL-C, and lipoprotein(a). We will also use a multivariable linear regression model with the outcome of the primary endpoints, adjusted for covariates that could be confounders such as age, gender, smoking, statin use/dose and relevant medical comorbidities. The primary endpoints will also be compared to an assumed value of 0% change in stenosis and PAV that would correspond to optimal medical management without a PCSK9 inhibitor. Although, some studies have suggested statin therapy can reduce carotid atherosclerosis, no such effect is known for ICAD. For this analysis, we will use linear mixed effects model to detect differences in the stenosis and PAV endpoints between patients taking Repatha or the presumed historical control values of 0% change. For the secondary endpoints, we will use logistic and linear regression depending on the nature of the variable and use the primary predictors of on-treatment LDL-C, HDL-C, and lipoprotein(a). For the exploratory endpoint of recurrent stroke, we will use the above mentioned methods as well as a Cox proportional hazards model for the endpoint of recurrent stroke with the observed rate in this study compared to controls matched according to degree to stenosis of the index artery. Due to differences in arterial structure and flow dynamics, there may be a more significant plaque reduction in certain intracranial vessels. We anticipate subgroup analyses, for example comparing change in stenosis or PAV in the middle cerebral artery versus the vertebral artery.

D.2. Power Analysis

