We power our study on the primary endpoint of change in stenosis and PAV. The GLAGOV trial showed 0.95% reduction in PAV for patients randomized to Repatha versus a 0.05% increase in PAV for patients in the placebo arm and was 78 weeks in length. Because the major intracranial arteries have a similar luminal diameter to coronary arteries, we may reasonably expect a 1% reduction in PAV for our 78 week study as documented in previous literature. Patients with intracranial atherosclerosis can be expected to have at least 3 additional sites of atherosclerosis, including extracranial arteries, that will be included in the series of PAV outcomes. Each subject will provide four sites of atherosclerosis and therefore, 4 PAV measurements. This cluster designed study will be modeled by a mixed effects linear regression to account for the cluster of arteries per patient. We obtain >80% power for our sample size of 150 patients, two-sided significance level 0.05, and a conservative assumed standard deviation of 4% from previous studies for the assumed 1% reduction in PAV against the documented control PAV of 0%.²³ With 150 patients, the minimum effect size possible to detect with 80% power is a 0.51% reduction. A 0.50% difference has been reported to be the cutoff to distinguish individuals that experience cardiovascular events versus those who do not.²³ Assuming a withdrawal rate of 25-30%, we would still reach >90% power for a 1% reduction with the above-listed conditions. We do not expect to show a significant reduction in recurrent stroke, but anticipate seeing a trend towards that outcome. This data could be used to accurately construct and power a subsequent trial with the primary outcome of recurrent stroke. Finally, in GLAGOV the linear relationship between change in stenosis, PAV and on-treatment LDL-C was very robust. We will be replicate this finding through means of a generalized linear mixed effects model. Our effective sample size may be sufficiently large enough to match the GLAGOV trial as each patient will be able to contribute an average of 4 arteries giving us an expected sample size between 800 and 1200 dependent on a conservative prediction of intra-class correlation. All reported p-values will be twosided and deemed significant at the 0.05 level.

D.3. Loss to Follow-up

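### D.1 defines the lipid model as a LOESS curve, in conflict with D.2, and states neither clustering nor unit of analysis for the covariate-adjusted and secondary models

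*Combined protocol and SAP*

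**What the plan says.** Section D.1 (Statistical methods) lists four kinds of model that matter here.

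- **Lipids and the primary endpoints.** "We will fit a mixed effects linear regression model, specifically a LOESS smoothing curve, to change in stenosis/PAV", with on-treatment LDL-C, HDL-C and lipoprotein(a) as the other variables.
- **Covariate adjustment.** "We will also use a multivariable linear regression model with the outcome of the primary endpoints, adjusted for covariates that could be confounders". The examples are age, gender, smoking, statin use or dose, and comorbidities.
- **Comparison with an assumed 0% change.** Here "we will use linear mixed effects model to detect differences in the stenosis and PAV endpoints between patients taking Repatha" and the historical value.
- **Secondary endpoints.** "For the secondary endpoints, we will use logistic and linear regression depending on the nature of the variable", with the on-treatment lipids as the main predictors.

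Only the first and third items mention mixed effects, and the first then equates the mixed model with LOESS. None of the four states the unit of analysis.

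Section D.2 (Power Analysis) counts four PAV measurements per patient and says: "This cluster designed study will be modeled by a mixed effects linear regression to account for the cluster of arteries per patient". On the relation with on-treatment LDL-C, which it wants to reproduce from the coronary trial, it says: "We will be replicate this finding through means of a generalized linear mixed effects model".

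**The concern.** A LOESS curve and a linear mixed model are different things. LOESS fits local regressions and returns a curve; it has no patient random effect and no single slope with a standard error. Because D.1 offers LOESS as the specific form of the mixed model, and not as a plot beside it, the sentence cannot be carried out as written. It also disagrees with D.2 on the same relation.

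The second issue is clustering. C.1 analyses every artery with at least 25% stenosis, and D.2 expects four per patient. Age, gender, smoking, statin use and on-treatment lipids take one value per patient. A regression that treats arteries as independent counts each of those values about four times, so its standard errors are too small whenever changes within a patient are correlated. D.1 asks for a mixed model by name in the 0% comparison but not in the covariate-adjusted or secondary models, so an analyst could fairly fit those without one.

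At stake are the covariate effects and the lipid associations with the secondary imaging endpoints. The protocol intends this dataset as the basis for a later randomized trial. Two conflicting specifications also leave the choice of lipid model open until the data are seen.

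**Working it through.** **1. The two sections side by side**

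| Analysis | D.1 | D.2 |
|---|---|---|
| Lipids and change in stenosis/PAV | Mixed linear model, defined as LOESS | Generalized linear mixed model (LDL-C) |
| Covariate-adjusted primary endpoints | Multivariable linear regression, clustering not stated | Only the general clustering sentence |
| Comparison with 0% change | Linear mixed model | Mixed linear regression |
| Secondary endpoints | Logistic or linear regression, clustering not stated | Not addressed |

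**2. Reproducing the plan's figure of 0.51%**

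Inputs from D.2: n = 150 patients, m = 4 sites each, SD 4%, two-sided 0.05, 80% power. The ICC is mentioned but given no value.

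Minimum detectable change = (1.960 + 0.842) × SD × √[(1 + (m − 1)·ICC) / (n·m)]

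- ICC = 0: 2.802 × 4 × √(1/600) = 0.457%.
- One site per patient: 2.802 × 4 × √(1/150) = 0.915%.
- To obtain 0.51%: effective n = (2.802 × 4 / 0.51)² ≈ 483. The design effect is 600/483 ≈ 1.243, so ICC = 0.243/3 ≈ 0.081 (0.073 to 0.089 allowing for rounding of 0.51).

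The stated figure is thus consistent with artery-level data and a small allowance for clustering, and it cannot be reached with one measurement per patient.

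**3. Type I error if arteries are treated as independent**

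For a predictor that is constant within a patient, the true variance of the slope is about 1 + (m − 1)·ICC times the one that unclustered regression reports. A nominal 5% test then has

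type I error = 2 × [1 − Φ(1.96 / √(1 + 3·ICC))]

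The check is a simulation of ordinary least squares under no effect, with four arteries per patient and 10,000 runs per setting. It used n = 150 and also n = 105, which is 150 × 0.70 after the 30% loss that D.2 allows for.

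| ICC | Design effect | Formula | Simulated, n = 150 | Simulated, n = 105 |
|---|---|---|---|---|
| 0.05 | 1.150 | 6.8% | not run | not run |
| 0.081 | 1.243 | 7.9% | 7.9% | 7.8% |
| 0.2 | 1.600 | 12.1% | 12.4% | 12.3% |
| 0.3 | 1.900 | 15.5% | 15.7% | 15.9% |
| 0.5 | 2.500 | 21.5% | 21.7% | 21.1% |

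Only 0.081 is tied to a figure in the plan; the other ICCs are assumptions. The number of patients hardly matters, because the inflation comes from the number of arteries per patient and the ICC.

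**4. What a patient random intercept does**

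With four arteries from every patient, testing a patient-level predictor in a random-intercept model amounts to regressing patient means on that predictor. Those means are independent, so the test returns to about 5%.

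**5. Limits of the calculation**

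It covers linear models with equal numbers of arteries. Logistic models for plaque enhancement would be affected in the same direction but were not simulated. Changes in cholesterol markers (secondary endpoint 2) are one value per patient and raise no artery clustering.

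**The case against.** A reader might infer that the p-values for LDL-C against the primary endpoints ignore clustering. The documents do not support that. D.2 names a generalized linear mixed model for exactly this relation, and that sentence states an analysis; it is not an input to the power calculation. The D.1 sentence cannot produce such a p-value either, since a LOESS curve has no slope to test. For this relation the defect is a misdefined analysis and a conflict between two sections, not shown inflation.

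It can also be said that D.2's general clustering sentence describes how the study will be modelled and so may cover the covariate-adjusted model. The word multivariable refers to the number of predictors and does not commit the analyst to independent errors. The unit is not stated, and C.1.a speaks of a composite outcome for stenosis, so a single summary per patient is conceivable; that would have no artery clustering. Finally, the main comparison with 0% change already has a mixed model.

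Most of this stands. The text is silent on clustering in those models; it does not rule clustering out. The inflation is therefore conditional, and its size rests on an ICC that the plan does not give. What the objection does not remove is the LOESS definition, the disagreement between D.1 and D.2, and the gap in the methods section, where D.1 asks for a mixed model in one analysis and omits it in the ones beside it.

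**Conclusion.** The point holds in three parts. D.1 misdefines the lipid analysis by equating LOESS with a linear mixed model. It conflicts there with D.2. It leaves clustering and the unit of analysis unstated for the covariate-adjusted primary models and the artery-level secondary models.

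If those regressions are fitted to arteries as worded, a nominal 5% test of a patient-level predictor has a true level of about 8% at the ICC implied by the plan's own 0.51%, rising to 15.5% and 21.5% at assumed ICCs of 0.3 and 0.5. This assumes four arteries per patient and independent errors in the fitted model. If the unit is a patient summary, this inflation does not arise. The comparison with 0% change, and the LDL-C relation as D.2 specifies it, are not affected. The plan should be corrected, but its primary inference is not in question on this ground.

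**What to change.** In D.1, replace the LOESS sentence and add the missing specification:

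- Change in stenosis and in PAV will each be analysed at artery level by a linear mixed model with a patient random intercept and fixed effects for on-treatment LDL-C, HDL-C and lipoprotein(a).
- The covariate-adjusted models use the same random intercept.
- Secondary endpoints measured per artery use a patient random intercept or patient-clustered standard errors.
- LOESS curves are descriptive plots only, with no inference drawn from them.

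Align D.2's sentence on the LDL-C relation with this model, and state there the ICC behind the 0.51%. The cost is a change of wording. The plan already uses a mixed model for the comparison with 0% change, and no further data or patients are needed.
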